9.1 Study design

This study will be a population-based retrospective cohort study on de-identified individual-level data extracted from registers and electronic medical records (EMRs) in Norway. It will be based on two partly overlapping cohorts of patients, one utilizing only nation-wide health

registers (called cohort 1) and one cohort based on EMR data from selected hospitals in Norway combined with registry data (cohort 2).

Warfarin has been the traditional treatment in Norway for many years, while dabigatran was marketed for NVAF patients from 1 July 2008, rivaroxaban from 1 February 2012 and apixaban from 15 February 2013. The three NOACs were granted Norwegian general reimbursement from 1 January 2013 (dabigatran and rivaroxaban) and 15 July 2013 (apixaban). The study period (i.e. from 1 January 2014) was defined to incorporate all use of the NOACs once they all had been under general reimbursement for at least 6 months.

Table 2: OAC marketing authorization dates and reimbursement dates for NVAF indication¹

ATC code	Drug	Marketed	NVAF Reimbursement
B01AA03	warfarin	4 October 1962	Early
B01AF02	apixaban	15 February 2013	15 July 2013
B01AF01	rivaroxaban	1 February 2012	1 January 2013
B01AE07	dabigatran	1 July 2008	1 January 2013

9.2 Setting

The study will be undertaken in Norway and will comprise all adult patients with NVAF who initiated treatment with either a NOAC or warfarin during the study period for the first time (OAC naïve first-time users). Study endpoints, discontinuation, switch to another OAC, death or end of study period will serve as censoring criteria.

The NVAF study population is defined in accordance with the 2018 European Heart Rhythm Association practical guide on the use of non-vitamin K antagonist oral anticoagulants in patients with atrial fibrillation, which define NOAC eligibility in NVAF patients as atrial fibrillation in the absence of rheumatic mitral stenosis or a mechanical heart valve.

Cohort 1 (registry study): Registries in Norway are nation-wide and provision of the information is mandatory, which eliminates the risk of both selection and re-call bias. The large and detailed dataset also makes it possible to adjust for other risk factors on which information is available.

In cohort 2, patients with NVAF diagnosis will be identified through extraction of patient-level data from EMRs from a number of hospitals in Norway, in order to describe these patients more closely regarding their clinical characteristics that are not available in nation-wide registers (e.g., in-patient treatments, anthropometric data and laboratory test results). This part of the

¹ Source: <http://www.legemiddelverket.no>

study is a pilot that will test the operational feasibility of accessing and linking the regional EMR data to the Norwegian Health Registers. Should the access to the regional EMR be granted, patients in cohort 2 will be identified and their EMRs extracted using the Pygargus Customized Extraction Platform (CXP). The extraction program has been used in a number of research projects since 2005 in the Swedish and Norwegian health care systems (6, 7). De-identified individual level data on age, gender, prescriptions, diagnoses, measures, laboratory tests, health care professional (HCP) visits, referrals, etc. can be collected from the EMRs into an encrypted database.

A key-code linked to each individual patient ID number will be extracted to enable linkage to national healthcare registers. This data will then be linked with the national registers data used in cohort 1. This key-code will be stored separate from the database used for analysis. Individual patient data from EMRs will then be linked to the described national registers (Norwegian Patient Registry, Norwegian Prescription Database and the Cause of Death Register). Extraction of patient level data will take place once and cover the period from 2009 to 2017 (or later depending on when EMR extraction can take place).

Datasets for cohort 1 and 2 will be de-identified before they are accessible for analysis. Neither Bayer nor other research partners will have access to patient-identifiable data. This is a legal prerequisite and is strictly enforced by the Registry Holders in Norway and is thoroughly reviewed during the application for an ethics approval. Furthermore, it is planned to store and analyze the datasets within the secure environment of "Services for sensitive data (TSD)" at the University of Oslo. TSD offers a secure environment for the collection, storage and analysis of sensitive research data.

9.2.1 Study time frame

For the main analysis, the study population will comprise all adult OAC naïve (no OAC prescription in the previous 365 days, counted from the date of the first dispensation backward to the end of OAC supply) NVAF patients in Norway dispensed a prescription for an OAC (NOAC or warfarin) for the first time in the study period (cohort 1a), defined as from 1 January 2014 to 30 June 2018 (or later depending on availability of data) and followed until endpoint of interest, the end of the study period or death. Patients will be censored at a switch or a discontinuation.

For exploratory analysis, a second study population (cohort 1b) will comprise all adult NVAF patients in Norway that did not receive an OAC (NOAC or warfarin) in the study period, defined as above.

The look-back period will be at least 5 years from the possible earliest index date of NOACs (1 January 2014) going back to 1 January 2009 (available data cut). The minimum follow-up period will be 1 month and the estimated mean follow-up time will be 18 months.

[figure not shown]

Figure 1: Study design

9.2.2 Selection criteria

Depending on the data source, the following 2 cohorts will be recruited:

Inclusion criteria

Registry cohort (Cohort 1)

Cohort 1a:

- Age ≥ 18 at the date of first OAC dispensation (index date)
- Diagnosed with atrial fibrillation or flutter in the period 5-year pre-index period. Defined as ICD10 codes; I480 (paroxysmal AF), I481 (persisting AF), I482 (chronic AF), I483 (typical AF), I484 (atypical AF) or I489 (unspecified atrial fibrillation or flutter) as given by either NPR **or** as a OAC (warfarin, dabigatran, rivaroxaban or apixaban) dispensed on the reimbursement code for AF in NorPD (ICD10 I48 or ICPC-2 K78)
- Dispensation of a first-time prescription for an OAC during the study period 1 January 2014 to 31 May 2018. This initiation of an OAC is the index event and requires that there is no previous prescription for any OAC in the preceding 365 days (counted from the date of the first dispensation backward to the end of OAC supply).

Cohort 1b:

- Age ≥ 18 at the beginning of the study period (1 January 2014).
- Diagnosed with atrial fibrillation or flutter prior or during the study period. Defined as ICD10 codes; I480 (paroxysmal AF), I481 (persisting AF), I482 (chronic AF), I483 (typical AF), I484 (atypical AF) or I489 (unspecified atrial fibrillation or flutter) as given by NPR.
- No dispensation of a prescription for an OAC (warfarin, dabigatran, rivaroxaban or apixaban) during the study period 1 January 2014 to 30 June 2018. The index event will be the beginning of the study period (1 January 2014) and requires that there is no previous prescription for an OAC in the preceding 365 days.

EMR cohort (Cohort 2):

- Age ≥ 18 at the date of first OAC dispensation (index date).
- Diagnosed with atrial fibrillation or flutter in the 5-year pre-index period defined as one of the following ICD10 codes in the EMRs obtained from the hospitals in the South-

Eastern Health Region; I480 (paroxysmal AF), I481 (persisting AF), I482 (chronic AF), I483 (typical AF), I484 (atypical AF) or I489 (unspecified atrial fibrillation or flutter).

- Dispensation of a first-time prescription for an OAC (warfarin, dabigatran, rivaroxaban or apixaban) during the study period 1 January 2014 to 31 May 2018. This initiation of an OAC is the index event and requires that there is no previous prescription of any OAC in the preceding 365 days (counted from the date of the first dispensation backward to the end of OAC supply).

Exclusion criteria (for both cohorts)

- Valvular atrial fibrillation defined as presence of ICD10 codes in NPR; I05.2 mitral stenosis with insufficiency, I05.8 other mitral valve diseases (mitral (valve) failure), I342 (non-rheumatic mitral valve stenosis), Z952 (presence of prosthetic heart valve) and procedure codes FKD (prosthetic replacement of mitral valve), FKA (Repair of mitral valve for stenosis), FKB (Annuloplasty of mitral valve for insufficiency), FKC (Repair of mitral valve for insufficiency), FKW (Other operations on mitral valve) and FMD (replacement of aortic valve).
- Deep Venous Thrombosis (DVT) as defined by ICD10 codes I80 (Phlebitis and thrombophlebitis), Pulmonary Embolism (PE) as defined by ICD10 code I26 or I82 (other venous embolism and thrombosis), Other venous embolism and thrombosis within last 6 months before index date.
- Knee and/or hip replacement surgery (NCSP procedure codes; NGB, NGC, NFB or NFC) 5 weeks before index date.

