appropriateness however of the reduced dosing could not be assessed due to the lack of clinical information. Another clear limitation of this study is the lack of effectiveness data and information on adherence.

Norway has a relatively homogenous and stable population of just over 5 million and a publicly funded healthcare system. Health-related data is systematically captured in electronic format in several registers, including National Health Registers that contain data on hospitalizations, prescriptions as well as causes of death of all inhabitants. Hospital and primary care Electronic Medical Records (EMRs) information are also available. Inhabitants of Norway have a unique personal identification number (PIN) which is used to link information from the various health registers.

Extraction of large amounts of data from EMRs is often a limiting factor. An automated data extraction tool available in Scandinavia (Customised eXtraction Program [CXP], IQVIA) was shown to efficiently and reliably extract EMR data from hospitals and primary care clinics across the country in full adherence to the data protection rules(5). This unique methodology automatically extracts structured and unstructured EMR data for large numbers of patients and assigns identifiers that make cross-linking with registry data possible on an individual patient level, while ensuring patient anonymity. The methodology of the CXP tool was developed in Sweden and it has been applied in primary care in Norway. However it has not yet been applied with Norwegian hospital EMRs.

8. Research questions and objectives

This population-based study offers a unique opportunity to assess both the effectiveness and safety of NOACs (rivaroxaban, dabigatran, apixaban) compared to warfarin in OAC naïve NVAF patients in Norway. In addition, this study will serve as a pilot project to evaluate the operational feasibility as well as the usefulness of linking the EMR data to the Norwegian Health Registers.

8.1 Primary objective:

- To assess the incidence rates of:
 - a. ischemic stroke (effectiveness)
 - b. intracranial hemorrhage (safety)

in OAC naïve NVAF patients who are dispensed individual NOACs for the first time and compare with the corresponding rates in OAC naïve users of warfarin in a propensity score matched population.

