Diuretics	NorPD	ATC code: C03	Co-variate
Beta-blockers	NorPD	ATC-code: C07	Co-variate
Calcium antagonists	NorPD	ATC-code: C08	Co-variate
Renin-angiotensin system drugs	NorPD	ATC-code: C09	Co-variate

Variable	data source	Definition	Relevance
Lipid-modifying drugs	NorPD	ATC-code: C10	Co-variate
Reduced or standard dose NOAC at index	NorPC	Indicator variable whether on reduced (15 mg riva, 2,5 mg api, 110 mg dabi) or standard (20 mg riva, 5 mg api, 150mg dabi) at index dispensation	Co-variate
Prior OAC use	NorPD	Previous OAC use. OAC availability (time of exhaustion of last dispensation) in 365 days prior to index dispensation. From the time of exhaustion of last dispensation and initiation of OAC in study period (> 12 months pre-index)	Co-variate
Previous bleeding hospitalization	NPR	ICD codes listed in section 9.3.4.2	Co-variate Included in mHASBLED
Modified HAS-BLED score	NPR and NorPD	
 - Hypertension defined by dispensation of at least one anti-hypertensive drug (see definition for hypertension above) last year prior to index date. 1 point - Renal impairment as defined by either hemodialysis (procedure code KAGD40) or kidney transplantation (procedure code KAS) or CKD stage 3 and 4 (ICD10 code N183, N184, N185). Expanded list of codes to define CKD will be considered as an option 2, 1 point - Liver impairment (ICD10 K70-K77). 1 point - Stroke during the last year prior to index visit (see definition). 1 point - Prior major bleeding (critical organ) last year before index date (see definition in 9.3.4.2) 1 point 	Bleeding risk score used as co-variate and effect modifier

Variable	data source	Definition	Relevance
		
 - Age \geq 65 years. 1 point - Therapy with either Nonsteroidal Anti-inflammatory Drugs (NSAID M01A) or anti-platelets (B01AC) in the previous year before index date. 1 point - Alcoholism (as defined by ICD10 codes above). 1 point 
Total HAS-BLED score from 0 to 8
	

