9.3.2 OAC exposure

New OAC exposure is defined as a single or series of dispensation of an OAC starting in the period from 1 January 2014 to end of study period. The duration of the observation period together with the pack size of each prescription will be used to calculate the length of a patient's OAC exposure. To ensure a minimum of one month follow-up data for all subjects on OAC treatment, inclusion (cut-off index OAC date) will be stopped one month before the end of available follow-up data.

For each dispensation, the OAC days of supply will be computed using information on date of dispensation, the number of packages and the pack-size dispensed. Since NOACs are prescribed in a fixed dose, the number of days of supply strictly corresponds to amount dispensed accounting for a recommended frequency of daily dosing. The NorPD contains information on tablet strength, pack-size and number of packages dispensed, and we assumed, according to the labelling, twice daily dosing for apixaban and dabigatran and once daily dosing for rivaroxaban, e.g. a patient supplied one package of a 100 tablet package of rivaroxaban will have a supply lasting for 100 days, whereas a 100 tablet package of apixaban will provide a supply lasting 50 days.

Computing the warfarin supply is not straightforward as we lack information on both dosing instructions and International Normalised Reference values (INR) in the registries.

Two different methods will be applied to compute the warfarin exposure;

1. EMR data (from cohort 2) holds information on both INR and dosing. Median mg/day of warfarin will be computed in relation to age (in 5-year categories) and gender (females and males). The median mg/day will be used as a basis for computing the warfarin supply in cohort 1.
2. Registry data (from cohort 1) using the length of each time interval in days between dispensation and corresponding dispensed warfarin amount for the time interval will be used to compute the median daily warfarin use for each patient. The calculated median mg/day for all patients using warfarin in the study period, in relation to age group and gender as with method 1, will subsequently be used in the computation of warfarin supply for each dispensation.

Similarly, the same methods will be used to set the end of OAC supply date during the pre-index period to be able to determine if a patient was OAC naïve or not (≥ 365 days without OAC supply prior to index date).

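### First-time OAC users are admitted on a 365-day washout, and the covariate that should identify former users is defined over two incompatible windows

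*Protocol*

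**What the plan says.** Section 9.2 says the study covers patients who "initiated treatment with either a NOAC or warfarin during the study period for the first time (OAC naïve first-time users"). The primary objective (Abstract and section 8.1) concerns OAC-naïve patients "who are dispensed individual NOACs for the first time", compared with OAC-naïve users of warfarin.

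The working rule is narrower. Section 9.2.2 (Cohort 1a, with near-identical text for Cohort 2) "requires that there is no previous prescription for any OAC in the preceding 365 days", counted back to the end of OAC supply. Section 9.2.1 gives the same definition. Section 9.3.2 uses modelled supply to "determine if a patient was OAC naïve or not (≥ 365 days without OAC supply prior to index date"). For warfarin, that end of supply is estimated from median daily doses by age group and sex.

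In Table 4 (section 9.3.1) the row Prior OAC use is labelled a covariate. It refers to "OAC availability (time of exhaustion of last dispensation) in 365 days prior to index dispensation" and then, in a sentence without a verb, to the time between exhaustion of the last dispensation and "initiation of OAC in study period (> 12 months pre-index").

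Section 9.2.1 sets a look-back of at least 5 years, to 1 January 2009.

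**The concern.** A 365-day gap in supply does not make a first-time user. Former users enter the new-user cohort, and the protocol appears to expect them, since a Prior OAC use covariate has no purpose otherwise.

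A patient who returns to OAC after a gap may differ from a true starter in ways that bear on intracranial haemorrhage and ischaemic stroke. The reason for stopping earlier may also influence whether warfarin or a NOAC is chosen next. If former users are unevenly spread across the arms and carry a different risk, the primary comparison is confounded by earlier OAC use. The natural protection is a covariate that flags these patients. As written, that row can be programmed in two ways, one of which gives a variable that is zero for nearly everyone.

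**Working it through.** **1. The two windows.** Let g be the number of days from the end of the last OAC supply to the index dispensation.

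| Rule | Source | Condition |
|---|---|---|
| Eligible as naïve | 9.2.2, 9.3.2 | g ≥ 365, or no earlier OAC |
| Prior OAC use, first window | Table 4 | supply within the 365 days before index, g ≤ 365 |
| Prior OAC use, closing fragment | Table 4 | g > 12 months |

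Eligibility and the first window overlap at most at g = 365. Eligibility and the closing fragment overlap for every former user seen in the look-back.

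Example: warfarin supply ends 31 December 2012 and the index is 1 March 2014. Then g = 365 + 60 = 425 days. The patient is eligible; the covariate is 0 on the first window and 1 on the second.

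**2. Can earlier use be seen?** From 1 January 2009 to an index on 1 January 2014 is 5.0 years, leaving 4.0 years beyond the washout. For an index on 31 May 2018 it is 9.4 years, leaving 8.4. Every patient therefore has at least 5 years of planned prescription history. Any dispensation in that history to an eligible patient must lie more than 12 months before index, because its supply ended at least 365 days before.

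**3. The plan's own figures.** Section 9.5: matched N = 70,000 × share × 0.90.
- dabigatran: 70,000 × 0.11 × 0.90 = 6,930
- apixaban: 70,000 × 0.17 × 0.90 = 10,710
- rivaroxaban: 70,000 × 0.19 × 0.90 = 11,970

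All three agree with Tables 7 to 10. No study-size figure is wrong on this point.

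**4. Size of bias (assumed inputs only).** Suppose there is no true effect. Let f_N and f_W be the shares of former users in the NOAC and warfarin arms, and r their event rate relative to true starters. The observed rate ratio is

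(1 − f_N + r·f_N) / (1 − f_W + r·f_W)

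| r | f_W | f_N | Ratio |
|---|---|---|---|
| 0.5 | 0.05 | 0.15 | 0.925/0.975 = 0.949 |
| 0.5 | 0.15 | 0.05 | 0.975/0.925 = 1.054 |
| 1.5 | 0.05 | 0.15 | 1.075/1.025 = 1.049 |
| 1.5 | 0.15 | 0.05 | 1.025/1.075 = 0.953 |
| any | 0.20 | 0.20 | 1.000 |

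None of these inputs is in the protocol.

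**5. Cost of restricting to 5 years without OAC.** Assume that 10% or 20% of the 70,000 are former users, spread evenly over the arms. Then 63,000 or 56,000 remain, and matched N (dabigatran / apixaban / rivaroxaban) is 6,237 / 9,639 / 10,773 or 5,544 / 8,568 / 9,576.

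Take the smallest arm, dabigatran, for intracranial haemorrhage at relative risk 1.00 and p = 0.0123. The interval is exp(±1.96·√(2(1 − p)/(pN))).
- N = 6,930: 0.74 to 1.35, as in Table 10
- N = 6,237: 0.73 to 1.37
- N = 5,544: 0.72 to 1.40

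**The case against.** The 365-day rule is stated openly and repeatedly as the meaning of OAC naïve. In section 9.2.1 the phrase about a first dispensation is tied to the study period, and in the objective it attaches to the NOAC. A one-year washout is a legitimate design choice. This stands: the conflict is with the first-time wording, chiefly in section 9.2, and does not show that the rule itself is wrong.

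A reader might infer that the covariate misses former users altogether. The row does not support that, because its closing fragment, read alone, would flag them. The defect is that two windows are given. Nor can one infer that the variable will be left out of the propensity score, since section 9.7 leaves the model detail to the SAP.

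A reader might also infer a demonstrated bias against NOACs: warfarin restarters as people who tolerated the drug, NOAC restarters as people who failed on it. If 5% to 15% are restarters, with haemorrhage hazards of 0.6 and 1.3 respectively, the ratio is inflated by 1.015/0.98 = 1.04 to 1.045/0.94 = 1.11. But the shares and the opposite-direction hazards are all assumed, with no adjustment. Warfarin restarters have also been without supply for a year, so they too stopped once. Previous bleeding hospitalisation, stroke and TIA are already covariates in Table 4. What remains unmeasured in Cohort 1 is INR control, because the registries hold no INR. Table 6 shows warfarin in 87,994 of 117,556 OAC users in 2013 (75%), but these are users in that year for all indications and say nothing direct about lapsed ones.

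Modelled warfarin supply is a minor issue. Counting from the end of supply is stricter than counting from the last dispensation. A patient still taking warfarin would look naïve only if a supply modelled at, say, 100 days lasted 465, a dose of about 22% of the median. Ordinary below-median dosing matters only near the 365-day boundary.

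**Conclusion.** The point holds as an inconsistency in definitions with an avoidable risk of confounding. The first-time description does not match a rule requiring only 365 days without supply, and Prior OAC use is given two windows that cannot both apply, one of them essentially empty by eligibility. This rests on the text alone.

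The size and direction of any bias cannot be derived. The range of 0.95 to 1.05 assumes a 10-point difference in former-user share between arms, a common relative rate of 0.5 or 1.5, and no adjustment. It is an illustration only. Replacing the main washout is defensible but not required. Repairing the covariate and testing the result in patients without earlier OAC is warranted, because the planned data allow it and section 9.9 does not list former users among the limitations.

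**What to change.** 1. In Table 4, define Prior OAC use as any OAC dispensation from 5 years to 12 months before index, recorded by drug, and delete the 365-day availability wording.
2. Include it in each of the three propensity score models.
3. Add a sensitivity analysis of ischaemic stroke and intracranial haemorrhage restricted to patients with no OAC dispensation at all in the 5 years before index, using dispensation dates rather than modelled warfarin supply.
4. Align the first-time wording in sections 9.2 and 9.2.2 and in the objectives with the 365-day definition. If the sponsor prefers, adopt the 5-year definition as the main rule and keep 365 days as the sensitivity analysis.
5. Report the number of former users by arm and by earlier drug, so that readers can judge how much this matters.

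The cost is a wording change, one derived variable and one extra analysis on a somewhat smaller cohort. It uses the look-back to 2009 that is already planned. Precision falls only modestly under the shares assumed above.

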8.3 Exploratory objectives (naïve OAC users)

- To compare demographic and clinical characteristics (age, gender, CHA₂DS₂-VASc and HAS-BLED score, bleeding history, concomitant medications and co-morbidities) and the incidence rates for ischemic stroke and intracranial hemorrhage in AF population that is not treated with OACs with AF population being treated with OACs.
- To investigate sub-groups of interest (patients > 75 years, renal impairment) in stratified analyses.
- To describe and compare adherence levels to NOACs among NVAF patients and assess whether different levels of adherence is associated with changes in the incidence rate of ischemic stroke and bleeding outcomes.
- To describe patient characteristics of NVAF patients receiving standard vs. reduced dose of NOACs and to estimate corresponding rates of ischemic stroke and bleeding
- To validate the diagnosis of NVAF, bleeding and stroke endpoints derived from the NPR data using EMR data.

9. Research methods

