9.2.3 Study population

Cohort 1 sampling:

The NorPD is a pseudonymized register which means that it is not possible to use dispensation of OAC as the starting point and as a source population. Being a pseudonymized register NorPD data needs to be the last register in the data collection that is linked to the other data sources. To circumvent this we will start with the Norwegian Census Register that will identify all Norwegian residents' of the age of 18 years and above during the study period. This dataset is sent to the NPR (for all patients with NVAF and without NVAF plus the relevant co-morbidities). Lastly, NorPD will identify all subjects with at least one OAC dispensation during the study period and link the registers (cohort 1a). A de-identified dataset with all NVAF patients having at least one OAC dispensed in the study period will be delivered to the research group (cohort 1a). Similarly, NorPD will identify all subjects that did not receive an OAC prescription during the study period and link the registers (cohort 1b). A de-identified dataset with all NVAF patients not having received an OAC prescription in the study period will be delivered to the research group (cohort 1b) for exploratory analysis.

[figure not shown]

Figure 2: Cohort 1 sampling procedure flow-chart

Cohort 2 sampling:

From the EMR extraction process all patients diagnosed with NVAf at selected hospitals in Norway between 2009 to the end of study will be selected. This cohort of patients will be linked with NPR and lastly NorPD will be added.

[figure not shown]

Figure 3: Cohort 2 sampling procedure flow-chart

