9.4 Data sources

For cohort 1 three data sources will form the basis for the analyses, the Norwegian Census Register (FRG), the Norwegian Prescription Database (NorPD) and the Norwegian Patient Register (NPR). The FRG list all Norwegian residents from birth to death, including migration data and place of birth.

The NorPD is a register covering all prescriptions dispensed at pharmacies nationwide and data is available from 1 January 2004. Each medication is coded according to the Anatomical Therapeutic Chemical (ATC) system. The prescription registry also includes information about date of dispensation, quantity dispensed, the defined daily dose (DDD) of the dispensed drug and strength. NorPD does not cover drug administered during hospital stays, drugs used at nursing home or over-the-counter drugs. From March 2007 the NorPD includes the reimbursement code using either the ICD10 or the ICPC-2 coding systems.

The NPR was established in 2008 and contains all hospital visits (emergency visits, in-patient hospitalizations and outpatient ambulatory consultations), length of stay and procedures (surgical and medical) from all hospitals in Norway. Diagnoses are coded according to the International Classification of Diseases, 10th revision (ICD10). Medical and surgical procedures are coded based on the NOMESCO (The Nordic Medico-Statistical Committee) coding system. Both primary and all subsequent codes related to each admission will be retrieved. Lag time in NPR is approximately 4 months.

The registries are nation-wide and provision of the information is mandatory, which eliminates the risk of both selection and recall bias. The large and detailed dataset also makes it possible to adjust for risk factors and analyze in depth the different sources of bias and confounding. The registry holders will generate the datasets and release it in a coded and de-identified form, but with a unique identifier common to the three datasets making individual merging of the NorPD, NPR and FRG datasets possible.

Data from the registries will be linked using the unique 11-digit national identification number. NorPD is a pseudonymized register and the registry holder will according to national guidelines handle the linkage and release the dataset in a coded form so that all participants remain de-identified.

The following key variables will be retrieved from FRG;

- Age
- Gender (male, female)

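### Cohort 1b treats the absence of a NorPD dispensation as absence of OAC treatment, although NorPD does not cover nursing homes (exploratory comparison only)

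*Protocol*

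**What the plan says.** Section 9.2.1 of the protocol describes the intended group: "a second study population (cohort 1b) will comprise all adult NVAF patients in Norway that did not receive an OAC". Section 9.2.2 makes this operational: "No dispensation of a prescription for an OAC (warfarin, dabigatran, rivaroxaban or apixaban) during the study period" (1 January 2014 to 30 June 2018), with no OAC prescription in the preceding 365 days either. Section 9.2.3 names the source that decides: "NorPD will identify all subjects that did not receive an OAC prescription during the study period". Everyone in cohort 1b has the same start: "The index event will be the beginning of the study period (1 January 2014").

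Section 8.3 uses the cohort to compare characteristics, risk scores and event rates "in AF population that is not treated with OACs with AF population being treated with OACs"; the events are ischemic stroke and intracranial hemorrhage.

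On the register itself, section 9.4 says: "NorPD does not cover drug administered during hospital stays, drugs used at nursing home or over-the-counter drugs". The variable list later in the same section includes a dispensation category with an institution level. The protocol does not explain how that level fits with the stated coverage.

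**The concern.** The cohort definition takes a missing record as proof of no treatment, in a register that by the protocol's own account cannot record one setting where elderly AF patients live. Someone with a hospital AF code who gets an OAC only from a nursing home meets every cohort 1b criterion, and no exclusion or flag in section 9.2.2 catches that person. The error falls on one side of the comparison.

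The NorPD-based covariates share the blind spot. In Table 4, the heart failure, hypertension and diabetes items of CHA2DS2-VASc come from NorPD. A resident with no community dispensing during the look-back can appear to have less comorbidity than is true, whether or not an OAC is being taken. At stake is whether the untreated group in section 8.3 is what its name says, and whether its recorded risk profile can be compared with that of cohort 1a.

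**Working it through.** **No figure to reproduce for the cohort.** The protocol gives no size, event rate or precision for cohort 1b, and no share of AF patients in nursing homes. The check is therefore a reading of the rules, followed by an illustration under stated assumptions.

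**Who is misclassified.** Entry to cohort 1b needs an AF code in the patient register (NPR), no NorPD OAC dispensation from 1 January 2014 to 30 June 2018, and none in the 365 days before. A resident with any pharmacy-dispensed OAC in those windows is kept out. The affected group is AF patients whose OAC in those windows was supplied only through an institution. The in-hospital gap adds little by itself: it matters only for patients given an OAC in hospital and never dispensed one afterwards.

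**Effect on the rate ratio.** Let m be the share of cohort 1b person-time that is in fact treated, and R the true treated/untreated rate ratio. Assume the misclassified patients have the treated group's rate. Then

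observed ratio = R / ((1 − m) + m × R).

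With R = 0.50 (assumed):

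- m = 5%: 0.50 / 0.975 = 0.513
- m = 10%: 0.50 / 0.950 = 0.526
- m = 20%: 0.50 / 0.900 = 0.556

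The same formula inverted, for other assumed values of the true untreated/treated ratio:

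| True untreated/treated ratio | m = 5% | m = 10% | m = 20% |
|---|---|---|---|
| 1.5 | 1.475 | 1.45 | 1.40 |
| 2.0 | 1.95 | 1.90 | 1.80 |
| 3.0 | 2.90 | 2.80 | 2.60 |

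Misclassification alone pulls the ratio towards 1. If OAC treatment lowers stroke and raises intracranial hemorrhage, unseen treatment lowers the apparent untreated stroke rate and raises the apparent untreated hemorrhage rate. Nursing-home patients are also likely to be frailer, which can move either rate. The documents offer nothing with which to size that.

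**Effect on CHA2DS2-VASc.** The items in Table 4 sum to the stated maximum: 1 + 1 + 1 + 2 + 2 + 1 + 1 = 9. The NorPD-based items are heart failure, hypertension and diabetes: 1 + 1 + 1 = 3. This is a ceiling, for two reasons:

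- Hypertension and diabetes are scored on a dispensation in the year before index. With index fixed at 1 January 2014, they are lost only if there was no qualifying community dispensation in 2013.
- The heart failure item has no one-year limit in Table 4, and section 9.6 looks back five years for comorbidity, so an earlier community prescription may recover it.

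The mean shortfall in cohort 1b is the share resident throughout the look-back times the points lost. With assumed shares of 5% to 20% and 1 to 2 points lost each, it lies between 0.05 × 1 = 0.05 and 0.20 × 2 = 0.40 points.

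**The case against.** The case for leaving the plan alone has weight. Cohort 1b serves only an exploratory objective, and the NOAC-versus-warfarin comparisons do not use it. Section 9.4 discloses the coverage gap, and section 9.9 concedes that exposure is measured from pharmacy dispensing and that actual intake is unknown. Analytical detail is left to the SAP, which is not at hand. Even with 10% of cohort 1b misclassified, an assumed ratio of 0.50 moves only to 0.53. All of this stands, and it limits the importance of the point.

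It does not remove it. The caveat in section 9.9 concerns dispensed drugs that may not be taken. The problem here is the reverse: drugs taken that are never recorded. Section 9.9 also presents the register coverage as complete and as eliminating selection bias, without drawing the consequence for a cohort defined by absence from NorPD. That definition is fixed in the protocol, so it is not a detail waiting for the SAP.

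A reader might infer that all OAC-treated residents in cohort 1b are under-scored, by three points. The documents do not support this. A patient admitted to a nursing home after 1 January 2014 and given an OAC there is wrongly labelled untreated, yet can have a correct baseline score. Residents who truly receive no OAC can be under-scored just as well. The two problems overlap but are distinct.

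**Conclusion.** The point holds for the exploratory comparison in section 8.3. As written, the cohort 1b rule identifies patients without a pharmacy-dispensed OAC, and the protocol presents them as patients without OAC treatment. The resulting misclassification arises in cohort 1b only. Under assumed shares of 5% to 20% and an assumed true ratio of 0.50, the observed ratio is about 0.51 to 0.56, a modest dilution. The loss of CHA2DS2-VASc points is a secondary effect, confined to people without community dispensing during the look-back and limited to three points.

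A reader might go further and conclude that the bias is large, that its net direction is known, or that it reaches the primary results. None of these follows. The share misclassified is not in the documents, frailty may offset or add to the dilution, and the primary comparison does not draw on cohort 1b. Nor is it established that NorPD holds no trace of residents, since the institution level in the dispensation category is unexplained.

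**What to change.** 1. Call cohort 1b AF patients with no pharmacy-dispensed OAC, in sections 8.3, 9.2.1 and 9.2.2 and in the tables.
2. Say in section 9.9 that institutional supply is invisible, that some treated residents will count as untreated, and that NorPD-based covariates may be incomplete for long-term residents.
3. Reconcile the two statements in section 9.4 on NorPD coverage and the institution category. If the category is informative, use it to flag residents.
4. Keep the planned cohort as the main exploratory analysis. Add a sensitivity analysis that restricts both cohorts to patients with at least one NorPD dispensation of any drug in the 365 days before index: before the patient's own index dispensation in cohort 1a, and calendar year 2013 in cohort 1b. Applying it to both sides avoids a one-sided selection.

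Censoring cohort 1b after a long run without any dispensing, for example 6 months, would address later admissions. Such a gap may itself follow a decline or an event, so the censoring could be informative; use it, if at all, only as a further sensitivity analysis.

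The cost is a few sentences and a little programming on NorPD data already requested for all drugs. The restricted analysis loses some healthy patients who fill no prescriptions, and it does not catch people who enter an institution after index.
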